**Table 9-1 Analysis Populations**

Population	Definition
Enrolled	All enrolled participants who sign informed consent
Safety	All participants who received $\geq 1$ administration of study intervention

Relamorelin

### 9.4. Statistical Analyses

The SAP will be developed and finalized before database lock and will describe the participant populations to be included in the analyses. This section is a summary of the planned statistical analyses:

Methodology	Description
Categorical counts	
 
• Number of participants in individual categories                             
 
○ Participants with <math>\geq 1</math> qualifying event counted once per individual category
 
 
 

Categorical descriptives	
 
• Number and percentage of participants in individual categories                             
 
○ Participants with <math>\geq 1</math> qualifying event counted once per individual category
 
 
 
• N1 if percentage denominator <math>\neq</math> number of participants in the population (standard percentage denominator)                             
 
○ N1 = participants with nonmissing baseline value
 
 
 

Continuous descriptives	
 
• N1, mean, SD, median, minimum, maximum
 
• N1 = participants with nonmissing value
 

Event descriptives	
 
• Number and percentage of events in individual categories                             
 
○ Events counted individually for each instance
 
 
 
• Percentage denominator = total number of events
 

CFB descriptives	
 
• Continuous descriptives for baseline, postbaseline, and change from baseline (CFB) values
 
• N1 = participants with nonmissing values at both baseline and the specified postbaseline analysis visit
 

Shift analyses	
 
• Number and percentage of participants in individual baseline and postbaseline categories
 
• Percentage denominator = number of participants in individual baseline categories
 
• N1 = participants with nonmissing values at both baseline and the specified postbaseline analysis visit
 

#### 9.4.1. Safety Analyses

The safety analysis will be performed using the safety population and will be fully defined in the SAP. No endpoints were specified for this study. The safety parameters will include AEs, vital signs, clinical laboratory tests (hematology, clinical chemistry including HbA1c, urinalysis), and ECG values reported as clinically significant AEs.

Relamorelin

#### 9.4.1.1. Adverse Events

An AE will be considered a TEAE if:

- The AE began on or after the date of the first dose of study intervention; or
- The AE was present before the date of the first dose of study intervention, but increased in severity or became serious on or after the date of the first dose of study intervention

An AE that occurs more than 30 days after the last dose of study intervention will not be counted as a TEAE.

An AE will be considered a TESAЕ if it is a TEAE that additionally meets any SAE criteria.

The number and percentage of participants reporting TEAEs will be tabulated by the MedDRA SOC and preferred term, and by SOC, preferred term, and severity (MedDRA version 21.0 or newer).

The number and percentage of participants reporting treatment-related TEAEs will be tabulated by SOC and preferred term.

If more than 1 AE is coded to the same preferred term for the same participant, the participant will be counted only once for that preferred term using the most severe occurrence for the summarizations by severity.

Summary tables will be provided for participants with TESAЕs and participants with TEAEs leading to discontinuation. Listings of all AEs, SAEs, and AEs leading to discontinuation by participant will be presented.

The definitions of an AE and SAE can be found in [Appendix 3](#).

#### 9.4.1.2. Clinical Laboratory Assessments

Descriptive statistics for clinical laboratory values (in SI units) at baseline and changes from baseline at each assessment will be presented for each clinical laboratory assessment.

The criteria for PCS laboratory values will be detailed in the SAP. The number and percentage of participants who have PCS postbaseline clinical laboratory values will be tabulated at each assessment. The percentages will be calculated relative to the number of participants who have available non-PCS baseline values and at least 1 postbaseline assessment. The numerator will be

Relamorelin

the total number of participants with at least 1 PCS postbaseline value. A supportive listing of participants with PCS postbaseline values will be provided for the safety population.

Shift tables from baseline to end of study for clinical laboratory parameters will be presented.

Study-specific assessments (eg, HbA1c) will be summarized as part of the overall clinical laboratory assessments.

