## Relamorelin

include: potentially life-threatening dehydration due to persistent vomiting, GERD that can advance to esophagitis, formation of bezoars, difficulty managing blood glucose levels, and malnutrition due to poor absorption of nutrients or a low-calorie intake ([US Department of Health and Human Services 2012](#)). Aside from the impact on patients, these events often lead to hospitalization ([Koch 2016](#)), resulting in a high economic burden for health care systems.

DG complicates management of blood glucose for both T1DM and T2DM patients due to carbohydrates being delivered to and therefore absorbed from the small intestine at unpredictable times ([Rayner 2001](#)). As a result, diabetic patients with DG often have poorly controlled diabetes, frequently with alternating hypo- and hyperglycemia, especially if treated with insulin.

Little data on the incidence and prevalence of GP are available; however, an older epidemiology study of diagnosed GP (defined as typical symptoms plus confirmed delayed GE by scintigraphy) showed prevalence of 24.3 per 100,000 inhabitants and incidence of 6.3 per 100,000 persons per year in Olmstead County, MN from 1996 to 2006 ([Jung 2009](#)). This study reported that age-adjusted prevalence of GP was approximately 4 times greater for women than men (37.8 vs 9.6 cases per 100,000 persons). It has been reported that 30% to 50% of diabetic patients have delayed GE, while the prevalence of the specific symptoms of GP (nausea and vomiting) is lower, with approximately 10% of patients with diabetes being affected ([Hopkins Medicine 2013](#)). According to [Bharucha \(2015\)](#), in a restricted community-based study of GP in DM, the average cumulative incidence of symptoms and delayed GE over 10 years was higher in T1DM (5%) than in T2DM (1%) and controls (1%). It is expected that the incidence of DG will increase worldwide in proportion to the increase in T2DM due to increasing prevalence of obesity.

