### 4.3. Justification for Dose

A RLM dose of 10 µg SC BID will be used, which is the same as the dose in the Phase 3 program.

This dose was selected based on clinical safety and efficacy data from Study RLM-131-009, which also provided PK and PD information for the 10 µg dose.

Study RM-131-009 was a 12-week Phase 2b, randomized, double-blind, placebo-controlled, parallel-group study to evaluate the safety and efficacy of RLM in diabetic participants with moderate to severe DG. The doses included within the study were 10 µg BID, 30 µg BID, and 100 µg BID. In general, all doses tested within Study RM-131-009 appeared to demonstrate meaningful reductions in overall DG symptom scores, including vomiting episodes, with acceptable safety and tolerability. The frequency of vomiting episodes was reduced from baseline over the 12-week treatment period to a similar extent for participants who received the 3 doses of RLM tested and placebo. Based upon the observed dose response of change-from-baseline symptom scores collected daily over the course of 12 weeks using the DGSSD, the 30 µg BID and 100 µg BID doses demonstrated apparent maximal effects, while the 10 µg BID dose achieved near maximal reductions. Of note, the twice-a-day regimen of RLM appears to be necessary for effective symptom relief; the 10 µg once daily study treatment did not demonstrate significant improvement in symptom relief compared with placebo after 28 days of dosing in Study RM-131-004.

Review of the safety laboratory data collected in RM-131-009 revealed a dose-related increase in HbA1c values. Although the variability in HbA1c response was high across all treatments, the 30 µg BID and 100 µg BID doses demonstrated an increase in HbA1c values that was approximately twice as much as observed for the 10 µg BID dose after 12 weeks of study. Shorter durations of treatment (4 weeks) with 10 µg BID of RLM, as observed in Study RM-131-004, did not demonstrate this increase in HbA1c in diabetic participants.

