## Relamorelin

- Adherence to the study design requirements, including those specified in the SoA, is essential and required for study conduct.
- The maximum amount of blood collected from each participant over the duration of the study, including any extra assessments that may be required, will be approximately 170 mL. Repeat or unscheduled samples may be taken for safety reasons or for technical issues with the samples.

All participants who roll over to this continued-access study (Study 3071-305-020) after completing their final visit assessments in either Study RLM-MD-03 or Study RLM-MD-04 are required to sign a new IC. Additionally, eligible participants who completed these studies prior to administrative initiation of this protocol at their study center, will be allowed to participate in this continued-access study, but are required to sign a new IC. Information from the final visit of Study RLM-MD-03 or Study RLM-MD-04 will be used as the information for Visit 1 (Baseline) of this study for these participants; if a participant enters this continued-access study > 30 days after last visit in lead-in study, Visit 1 baseline assessments will be completed (See SoA, Section 1.3). Demography and ongoing medical history will also be rolled over from Studies RLM-MD-03 or RLM-MD-04.

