#### **9.4.1.3. Vital Signs**

Descriptive statistics for vital signs (systolic and diastolic BP, pulse rate, weight, respiration rate, and temperature) at baseline (screening) and changes from baseline at each assessment will be presented.

Vital sign values will be considered to be PCS if they meet both the observed-value criteria and the change-from-baseline-value criteria that will be detailed in the SAP. The number and percentage of participants who have PCS postbaseline vital sign values will be tabulated for each assessment. The percentages will be calculated relative to the number of participants who have available non-PCS baseline values and at least 1 postbaseline assessment. The numerator will be the total number of participants with at least 1 PCS postbaseline value. A supportive listing of participants with PCS postbaseline values will be provided for the safety population.

Shift tables from baseline to end of study for vital signs will be presented.

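### Laboratory PCS percentage: the numerator counts participants whom the denominator excludes, so the rate is inflated whenever abnormality predates baseline

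*Protocol*

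**What the plan says.** Protocol Section 9.4.1.2 (Clinical Laboratory Assessments) sets out the PCS table in three consecutive statements:

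- Level of tabulation: "The number and percentage of participants who have PCS postbaseline clinical laboratory values will be tabulated at each assessment".
- Denominator: "The percentages will be calculated relative to the number of participants who have available non-PCS baseline values and at least 1 postbaseline assessment".
- Numerator: "the total number of participants with at least 1 PCS postbaseline value".

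The only item this section hands to the SAP is the set of thresholds: "The criteria for PCS laboratory values will be detailed in the SAP". The fraction itself is stated in the protocol. Section 9.4.1 adds, in general terms, that the SAP will define the safety analysis in full. The SAP was not available for this review.

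Section 9.4.1.3 uses the same construction for vital signs: "The numerator will be the total number of participants with at least 1 PCS postbaseline value".

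**The concern.** Removing participants with a PCS baseline from the denominator only makes sense if the table is meant to show PCS values that arise during the study. The numerator sentence does not carry that restriction. It admits two groups that the denominator leaves out: participants already PCS at baseline who are PCS again, and participants with no baseline value who have a later PCS value. Both push the percentage up and neither can pull it down.

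PCS values at baseline are plausible here, most of all for glycemic parameters:

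- Section 2 says that "diabetic patients with DG often have poorly controlled diabetes, frequently with alternating hypo- and hyperglycemia".
- Membership of the safety population (Table 9-1) depends only on dosing, not on baseline laboratory status.
- Under Sections 4.1 and 8, participants who roll over within 30 days take their baseline from the last lead-in visit. Those lead-in studies were placebo-controlled, so some participants will already have been on RLM at baseline. Participants who enter later than 30 days have a fresh baseline.
- Section 4.3 reports: "Review of the safety laboratory data collected in RM-131-009 revealed a dose-related increase in HbA1c values". The same section says the rise at 10 µg BID, the dose used here, was about half that at the two higher doses.

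The parameters most exposed to the error may thus be those of most safety interest. In a single-arm study whose sole objective is safety, no comparator would reveal that a rate is inflated.

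There is a second, smaller problem. The table is called for at each assessment, yet both parts of the fraction are defined over the whole postbaseline period. The text does not settle whether one overall percentage per parameter or a percentage per visit is wanted.

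**Working it through.** **Inputs.** The protocol states no PCS rate, no PCS threshold and no baseline PCS frequency, so there is no figure of its own to reproduce. From the protocol: the definitions in Section 9.4.1.2 and the planned size of about 1000 (Section 4.1). Assumed: b, s and i below, and that every participant has a postbaseline value.

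**Notation.** For one laboratory parameter, with N participants:

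- b = share PCS at baseline
- s = share of those who are PCS at least once afterwards
- i = incidence of PCS among participants not PCS at baseline

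**Formulas.**

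- Denominator: N(1−b)
- New cases: N(1−b)i
- Persisting cases: N·b·s
- Matched rate: N(1−b)i / N(1−b) = i
- Rate as written: [N(1−b)i + N·b·s] / N(1−b) = i + b·s/(1−b)
- Excess: b·s/(1−b), which is never negative and is zero only if b·s = 0

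Participants with a missing baseline and a later PCS value would add to the excess. They are left out of the figures below.

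**Worked counts at N = 1000, b = 10%, s = 80%, i = 10%.** The denominator is 900. New cases are 900 × 0.10 = 90 and persisting cases 100 × 0.80 = 80. Matched rate: 90/900 = 10.0%. As written: (90 + 80)/900 = 170/900 = 18.9%.

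**Excess in percentage points** (does not depend on i):

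| b | s = 50% | s = 80% | s = 90% |
|---|---|---|---|
| 0% | 0 | 0 | 0 |
| 1% | 0.51 | 0.81 | 0.91 |
| 5% | 2.63 | 4.21 | 4.74 |
| 10% | 5.56 | 8.89 | 10.0 |
| 20% | 12.5 | 20.0 | 22.5 |

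**Rates as written, s = 80%.** With i = 5%: 5.8% at b = 1% and 9.2% at b = 5%. With i = 10%: 18.9% at b = 10% and 30.0% at b = 20%.

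**Boundedness.** With b = 60%, s = 80%, i = 5% and N = 1000, the denominator is 400 and the numerator 20 + 480 = 500, giving 125%. This is an extreme setting, used only to show that the ratio is not a proportion.

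**Vital signs.** Section 9.4.1.3 requires both an observed-value and a change-from-baseline criterion. A postbaseline value there counts only if it has moved from baseline, so the laboratory argument does not carry over directly, and no inflation is claimed.

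**The case against.** The best defence is that the intent is clear. A percentage taken relative to a defined set is naturally read as counting members of that set, and the numerator sentence may be only a counting rule (each participant once), in line with the methodology table in Section 9.4. Section 9.4 also calls itself a summary, and the SAP may restrict the numerator. That is a fair reading of what was meant. It is not what the numerator sentence says: it refers to the total number of participants, and nothing else in the protocol narrows it. A SAP that follows the text carries the error forward; one that corrects it departs from the text.

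The size is also open to challenge, and that part stands. Incidence, b and s are all assumed. The protocol does not say that HbA1c or glucose will have a PCS criterion, and poor control does not by itself show that values cross an unstated limit. For analytes where baseline PCS is rare, the excess is under one point.

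On the by-visit question, the section sometimes uses the word assessment for a laboratory parameter, so an overall table per parameter is a possible reading. It is not the only one, so the ambiguity remains.

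Finally, no hypothesis test or decision rule uses this percentage. The shift tables, the change-from-baseline summaries and the listing of PCS participants would let a careful reader separate new from persisting abnormality. They reduce the harm but leave the tabulated percentage uncorrected.

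**Conclusion.** The concern holds. As written, the numerator is not a subset of the denominator. The laboratory PCS percentage is biased upward whenever anyone outside the denominator has a postbaseline PCS value, and it is correct only when no one does. The direction follows from the definitions alone.

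The amount rests on assumed values of b and s, and cannot be narrowed until the PCS thresholds and baseline data are known. It could be negligible for most analytes and material for parameters that are often abnormal at entry. This should be fixed: it distorts a safety rate in an uncontrolled safety study, although no inference depends on it.

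**What to change.** In Section 9.4.1.2, replace the numerator and denominator sentences with wording such as:

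> For each parameter, the denominator is the number of participants whose baseline value is non-missing and not PCS and who have one or more postbaseline values for that parameter. The numerator is the number of those same participants with one or more PCS postbaseline values for that parameter.

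Then state whether the table is overall or by visit. If it is by visit, limit both numerator and denominator to participants with a non-PCS baseline and a non-missing value at that visit.

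Use the same numerator wording in Section 9.4.1.3, for consistency only.

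The cost is one or two sentences in the protocol, carried into the SAP and the table programming. No additional data are needed.

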### **6.5. Concomitant Therapy**

Any medication or vaccine (including over-the-counter or prescription medicines, vitamins, and/or herbal supplements) that the participant is receiving at the time of enrollment or receives during the study must be recorded on the eCRF along with:

- Reason for use
- Dates of administration including start and end dates
- Dosage information including dose and frequency

Prior medications that were ongoing at the end of Studies RLM-MD-03 and RLM-MD-04 will be automatically transferred into the Study 3071-305-020 database.

As much as possible, the dose and frequency of all concomitant medications taken for chronic conditions with the exception of DM are to be held stable during the study. The sponsor is to be contacted if there are any questions regarding concomitant or prior therapy. Diabetic medications will be adjusted as needed to keep glycemic control at a steady level (Section 6.5.2).

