### 7.1.2. Permanent Discontinuation

Permanent discontinuation of study intervention also requires discontinuation from the study. The following criteria should be evaluated:

- Special consideration should be paid to the appearance of abnormal laboratory test results suggesting severe drug-induced liver injury (DILI). Discontinuation of study intervention for abnormal liver function should be considered by the investigator when a participant meets criteria for Hy's law (see Section 8.3.7.1 and Appendix 9) or if the investigator believes that it is in the best interest of the participant.
- Documented episode of diabetic ketoacidosis, hyperosmolar non-ketotic diabetic syndrome, or severe hypoglycemia (defined as glucose levels < 3mmol/L, or < 54 mg/dl) that are assessed as study treatment-related.
- Female participants who become pregnant during the study must be discontinued from study intervention immediately and withdrawn from the study. See Appendix 7 for further details regarding follow-up of the participant through the pregnancy.

See the SoA (Section 1.3) for data to be collected at the time of study intervention discontinuation.

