### 8.2.4. Clinical Safety Laboratory Assessments

- See [Appendix 2](#) for the list of laboratory tests to be performed and the SoA (Section 1.3) for the timing and frequency.
- The investigator must review the laboratory report, document this review, and record any clinically significant changes occurring during the study in the AE eCRF. The laboratory reports must be filed with the source documents. Clinically significant abnormal laboratory findings are those which are not associated with the underlying disease, unless judged by the investigator to be more severe than expected for the participant's condition.
- All laboratory tests with abnormal values considered clinically significant during participation in the study or within 30 days after the last dose of study intervention must be repeated until the values return to normal or baseline or are no longer considered clinically significant by the investigator or MSP.
  - If such values do not return to normal/baseline within a period of time judged reasonable by the investigator, the etiology is to be identified and the sponsor notified.
  - All protocol-required laboratory assessments, as defined in [Appendix 2](#), must be conducted in accordance with the laboratory manual and the SoA (Section 1.3).
  - If laboratory values from non-protocol specified laboratory assessments performed at the institution's local laboratory require a change in participant management or are considered clinically significant by the investigator, then the results must be recorded in the eCRF as AEs/SAEs.
  - Urine dipstick kits are to be used to conduct pregnancy tests.

Relamorelin

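### The laboratory shift tables use only the end-of-study value, so shifts that reverse earlier, and worsening from an already abnormal baseline, are thinly displayed; a worst on-treatment shift should be added

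*Protocol*

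**What the plan says.** Section 9.4.1.2 fixes the laboratory shift display: "Shift tables from baseline to end of study for clinical laboratory parameters will be presented." Section 9.4.1.3 does the same for vital signs: "Shift tables from baseline to end of study for vital signs will be presented." The methods table in section 9.4 takes each participant's own baseline category as the percentage denominator and defines the participants counted as "N1 = participants with nonmissing values at both baseline and the specified postbaseline analysis visit". Neither section names a shift to the worst value.

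Three other provisions affect what the last value shows:

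- Section 8.2.4: laboratory tests with clinically significant abnormal values "must be repeated until the values return to normal or baseline or are no longer considered clinically significant by the investigator or MSP".
- Section 6.5: "Diabetic medications will be adjusted as needed to keep glycemic control at a steady level".
- Section 7.1.2: "Permanent discontinuation of study intervention also requires discontinuation from the study".

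Section 9.4.1.2 also plans change from baseline at each assessment, a PCS table whose numerator is "the total number of participants with at least 1 PCS postbaseline value", and a listing of participants with PCS post-baseline values. The PCS percentage uses participants with a non-PCS baseline and at least one post-baseline assessment. PCS criteria are left to the SAP. Clinically significant laboratory changes go to the adverse event form (8.2.4), and treatment-emergent events are tabulated (9.4.1.1).

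**The concern.** Safety is the only objective (section 3). In section 2, the signal that the sponsor itself describes is worse glycemic control, seen as rising HbA1c and fasting glucose. A shift table answers a question that by-visit means cannot: how many individuals moved from one category to another, starting from each baseline category. Here it is tied to a single late value.

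The protocol's own procedures tend to bring that value back towards baseline, especially for glucose and HbA1c, where treatment is adjusted in response. A participant who moved up a category in the second year and was treated back by the final visit is counted as unchanged.

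The PCS table looks at any post-baseline value, but its denominator leaves out participants who are PCS at baseline. In a diabetic population these may be the people in whom further glycemic worsening matters most. How many there are depends on thresholds that the protocol does not give.

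**Working it through.** The protocol states no figure on this point, and the study has no sample size or power calculation to reproduce. The check is a comparison of displays, followed by an illustration under assumed inputs.

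**Which planned display shows which kind of laboratory change**

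- *Reaches PCS, participant non-PCS at baseline, later resolves.* Shown by the PCS count, the PCS listing and the by-visit summaries. Missing only from the shift table.
- *Judged clinically significant, later resolves.* Recorded as an adverse event and tabulated if treatment-emergent. Missing only from the shift table.
- *Changes category but stays below PCS, not judged clinically significant, later reverses.* Reflected only in by-visit means and medians, where an individual shift cannot be seen.
- *Already PCS at baseline and then worsens.* Outside the PCS denominator. The listing, as worded, can still include the participant, and an adverse event can be recorded. The shift table starts from every baseline category, but shows the worsening only if it persists to the last value and the categories are fine enough to separate abnormal from more abnormal.

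The last two lines are the gap.

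**Illustration 1: episodes with a duration**

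All inputs are assumptions: episode rate r = 0.10 per year, mean duration d = 0.25 or 1 year, follow-up t = 3 years.

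- Ever abnormal: 1 − exp(−r·t) = 1 − exp(−0.30) = 25.9%.
- Abnormal at the end (long-run share): r·d/(1 + r·d).
  - d = 0.25: 0.025/1.025 = 2.4%.
  - d = 1: 0.10/1.10 = 9.1%. Starting free of abnormality, the value at 3 years is 9.1% × (1 − exp(−1.1 × 3)) = 8.8%.

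The Amendment 2 summary describes laboratory tests every 3 months. If that interval held throughout, 3 years would give 12 post-baseline samples, of which the shift table uses 1 (1/12 = 8.3%).

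**Illustration 2: independent abnormality at each visit**

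Assumed probability p at each of k visits. Ever abnormal is 1 − (1 − p)^k; abnormal at the last visit is p.

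| p | k | ever | last visit |
|---|---|---|---|
| 2% | 4 | 7.8% | 2% |
| 2% | 8 | 14.9% | 2% |
| 5% | 4 | 18.5% | 5% |
| 5% | 8 | 33.7% | 5% |

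Both models point the same way. For transient abnormalities, an end-value table cannot show more participants than were ever affected, and usually shows fewer. Where the abnormality reaches PCS level, the planned any-post-baseline count already reports the ever figure among participants non-PCS at baseline. The contrast therefore measures an actual loss only for the gap identified above.

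**The case against.** The strongest case on the other side is that the other displays already do this work. The repeat rule applies only to abnormalities judged clinically significant, and the same section sends those to the adverse event form. Section 8.3.7.2 also requires clinically significant hyperglycemia and hypoglycemia to be reported, and section 10.3.1 makes inadequate diabetes control an event of special interest. This stands, and it limits the point to a gap in presentation. It is not complete: sections 8.2.4 and 10.3.1 set aside findings associated with the underlying disease unless they are more severe than expected, and that is a judgement.

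It can also be said that an end-of-study shift is a legitimate display in an extension study, because it shows persistence, and that the SAP may add tables. Both are true. The end-of-study table should stay. But section 9.4.1.2 names the time point itself, and a comparison with one specified visit does not describe a worst value across visits and repeats.

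Four stronger readings are tempting and not supported:

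- *Transient toxicity disappears from the safety report.* It does not; it is absent from the shift tables.
- *Vital signs have the same problem for the same reason.* The repeat-until-resolved rule covers laboratory tests only, and section 8.2.2 has no counterpart.
- *The PCS table rests on a single cut-off.* Laboratory criteria are left to the SAP, and vital signs need both an observed-value and a change criterion.
- *The last value is generally off drug.* Stopping drug means leaving the study, so a post-dosing last value is possible. The protocol does not say which value counts as end of study, and the SAP may settle this.

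**Conclusion.** The point holds in a limited form, for laboratory tables. The only planned laboratory shift is to a late value that the study's own procedures tend to normalise. Transient or treated shifts that are below PCS level or not judged clinically significant, and worsening in participants already PCS at baseline, are poorly shown.

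The size cannot be taken from the protocol. The figures of 26% ever against 2.4% to 9% at the end rest wholly on assumed incidence, duration and follow-up. A reader might take them as the amount of toxicity that would go unreported. They are not, because any part reaching PCS level in participants non-PCS at baseline, or recorded as an adverse event, is reported elsewhere. Only the direction for transient changes is firm. The change is worth making because safety is the sole objective and the data are already collected.

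**What to change.** In section 9.4.1.2:

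- Add a shift table from baseline to the worst on-treatment post-baseline value, highest and lowest where both directions matter, including unscheduled repeats.
- Give a second version limited to the first 12 months, so that length of follow-up has less influence.
- Keep the baseline-to-end-of-study table beside it to show persistence or resolution. The worst-value table should not replace it.
- For glucose and HbA1c, use shift categories fine enough to show worsening from an already abnormal baseline.

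The same addition in section 9.4.1.3 for vital signs is optional.

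The cost is a few more tables. The worst-value percentages will look less favourable, will rise with the number of visits, and have no control arm to be compared with. A footnote to the tables should say so.
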